2.6.1 Efficacy Analysis for Dose De-Escalation

Virologic response by Day 14 for participants in Arm B cohorts will be assessed. For the purposes of dose de-escalation in the Arm B cohorts, a virologic response to the study treatment will be defined as having an HIV-1 RNA reduction of at least $1.0 \log_{10}$ copies/mL from baseline. With that definition, the dose de-escalation criteria for an Arm B cohort are:

- a. At least 3 participants with a virologic response by Day 14 **OR**
- b. If only 2 participants have a virologic response by Day 14, 6 additional participants will be enrolled in the same dose cohort, and at least 6 of the 12 participants show a virologic response by Day 14.

Evaluation of Arm B cohorts will not be impacted by this interim efficacy look.

3 Outcome Measures

3.1 Primary Outcome Measures

Per protocol section 10.2.1, the primary outcome measures are as follows:

3.1.1 Safety and tolerability

Occurrence of a Grade ≥ 3 AE that is related to study treatment (as judged by the CST, blinded to active/placebo treatment in Arms A and C) any time from study treatment administration through the entire follow-up (**36 weeks after the final infusion** for Cohort 4 and 24 weeks for other cohorts).

3.1.2 Pharmacokinetics

AUC_{12wk} of SAR441236 (see protocol section 11.0)

3.1.3 Efficacy

Change in plasma HIV-1 RNA (\log_{10} copies/mL) from baseline (defined as the last measurement taken prior to treatment initiation) to Day 7 of monotherapy for viremic participants with HIV (Arm B cohorts).

3.2 Secondary Outcome Measures

Per protocol section 10.2.2, the secondary outcome measures are as follows:

1. Plasma HIV-1 RNA (copies/mL) at baseline and post-infusion for viremic participants with HIV (Arm B Cohorts).
2. Change in plasma HIV-1 RNA (\log_{10} copies/mL) from baseline (defined as the last measurement taken prior to treatment initiation) to Day **7** and Day **14** of monotherapy, and maximum reduction during **14** days of monotherapy for viremic participants with HIV (Arm B cohorts).
3. Attributions of anti-SAR441236 antibodies in all cohorts.
4. Change in CD4+ T-cell counts (cells/mm³) from baseline to week 12 following single dose of SAR441236 for all cohorts and the change in CD4+ T-cell counts (cell/mm³) from baseline to week 12 following each infusion for Cohort 4.
5. Pharmacokinetic parameters (see protocol section 11.0) of SAR441236 following each infusion or SC injection.
6. Establish concentration (or dose)-response relationship between SAR441236 exposure and changes in plasma HIV-1 RNA from entry baseline to week **2** (or viral load nadir) for Arm B cohorts.

4 Statistical Principles

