2.2 Regimen

Double-blind randomization in Arms A and C will be 2:1 SAR441236:placebo. Arm B participants will all receive open-label SAR441236.

Arm A (Treated, virologically suppressed)

- Cohort 1: 1 mg/kg of SAR441236 or saline placebo administered as a single intravenous (IV) infusion. Cohort 1 enrollment was completed under Protocol Version 2.0.
- Cohort 2: 3 mg/kg of SAR441236 or saline placebo administered as a single IV infusion. Cohort 2 enrollment was completed under Protocol Version 2.0.
- Cohort 3: 10 mg/kg of SAR441236 or saline placebo administered as a single IV infusion. Cohort 3 enrollment **was completed** under Protocol Version 2.0.
- Cohort 4: 30 mg/kg of SAR441236 or saline placebo administered as an IV infusion every 12 weeks for a total of four infusions. Cohort 4 enrollment **began** under Protocol Version 2.0 **and completed under Protocol Version 3.0**.

Arm B (HIV viremic)

- Cohort 5: 1 mg/kg of SAR441236 administered as a single IV infusion. **Cohort 5 enrollment began under Protocol Version 2.0 and was closed with Protocol Version 3.0.**
- Cohort 7: 10 mg/kg of SAR441236 administered as a single IV infusion. **Cohort 7 never opened to enrollment.**
- Cohort 8: 30 mg/kg of SAR441236 administered as a single IV infusion. **Cohort 8 enrollment began under Protocol Version 3.0. No additional participants enrolled under Protocol Version 4.0.**

In protocol Version 4.0, participants in Arm B will initiate or re-initiate combination non-study-provided ART on Day 14.

Arm C (ART-treated, virologically suppressed)

- Cohort 10: 0.3 mg/kg of SAR441236 or saline placebo administered once via a single subcutaneous (SC) injection on a single day.
- Cohort 11: 1 mg/kg of SAR441236 or saline placebo administered once via single or multiple SC injections on a single day.

Figure 1: Schema Arm A

[figure not shown]

Figure 2: Schema Arm B

[figure not shown]
[figure not shown]

Figure 3. Schema Arm C

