2.4.2 Secondary Objectives

1. To evaluate the dynamics of plasma HIV-1 RNA decay in viremic participants receiving SAR441236 (Arm B).
2. To evaluate the antiviral activity of a single dose of SAR441236 at Day 14 and Day 28 and the maximum antiviral activity of a single dose of SAR441236 from baseline to Day 28 in viremic participants (Arm B).
3. To evaluate if anti-SAR441236 antibodies are induced after single or multiple doses.
4. To evaluate the effects of single and multiple doses of SAR441236 on CD4+ T-cell counts.
5. To establish concentration (or dose)-response relationships between SAR441236 exposure and changes in plasma HIV-1 RNA from entry to week 4 (or viral load nadir) in Arm B.

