4.2.2 Analysis of Secondary Outcomes

- **Plasma HIV-1 RNA (\log_{10} copies/mL) at baseline and post-infusion for treatment-naïve, viremic participants with HIV (Arm B cohorts)**

Longitudinal participant-specific plots for antiviral activity before initiation of ART will be presented for each participant in Arm B. **Given the little evidence of viral decay in Cohort 5 and the limited sample size in Cohort 8 (n=2), the planned modelling for viral decay will not be conducted.**

- **Change in plasma HIV-1 RNA (\log_{10} copies/mL) from baseline (defined as the last measurement taken prior to treatment initiation) to Day 7 and Day 14 of monotherapy, and maximum reduction during 14 days of monotherapy for treatment-naïve, viremic participants with HIV (Arm B cohorts)**

Similar analyses described in section 4.2.1 for the primary efficacy endpoint at Day 7 will be conducted for the Day 14 results. Summary statistics will be provided for the maximum reduction of each participant by dose cohort during monotherapy of SAR441236 (post-infusion and before ART initiation). **Protocol Version 4.0 considers the maximum reduction during 14 days of monotherapy because the timing for ART initiation/re-initiation was changed from “by 28 days” (Version 3.0 or earlier) to “at 14 days” for Arm B participants. However, since no participants enrolled under Version 4.0, we consider maximum reduction occurring in up to 28 days of monotherapy for Arm B participants.**

- **Attributions of anti-SAR441236 antibodies in all cohorts.**

The ADA status of participants exposed to anti-SAR441236 antibodies will be tabulated by scheduled visit day/week. Details of participants who developed anti-SAR441236 antibodies will be provided.

- **Change in CD4⁺ T-cell counts (cells/mm³) from baseline to week 12 following single dose of SAR441236 for all cohorts and the change in CD4⁺ T-cell counts (cells/mm³) from baseline to week 12 following each infusion for Cohort 4.**

Longitudinal participant-specific plots and numerical summaries for change from baseline in CD4⁺ T-cell counts (cells/mm³) will be presented by cohort.

- **Pharmacokinetic parameters of SAR441236 following each infusion.**

Descriptive numerical summaries of the following PK parameters (protocol section 11.3) by dose cohort will be presented:

Single dose:

- Maximum concentration (C_{max})
- Time of maximum concentration (T_{max})
- Dose-normalized maximum concentration
- Terminal half-life

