- Analysis windows have been widened to capture as much information as possible. For participants who received their infusion shortly before the pause, they were directed to the Single Dose Arm A SOE (Table 6.1-1 in Protocol Version 2.0) after they had reached Week 4 to reduce site burden. This will cause slight differences in visit schedules across Cohort 4 participants. However, the majority of these were virtual (no lab data collected) so the need to align lab results (e.g., CD4+ T-cell counts) will be negligible.

Arm B Single Dose Cohort (5) Considerations

- Four participants were on-study in Cohort 5 during the COVID-19 pause. One participant had completed the specified 24-week follow-up and was off study before the pause. All participants had reached Day 28 and initiated ART by the end of February 2020.
- **IMPACT: MODERATE**
 - There is no impact to the primary efficacy outcome (i.e., all participants had reached Day 28 before the COVID-19 pause) nor to any secondary outcome involving HIV-1 RNA.
 - The primary PK endpoint has the potential to be affected as some Week 12 visits were conducted virtually (and thus no labs were collected). The A5377 team pharmacologist will make the appropriate accommodations in the calculation of the PK parameters and document them in the PK analysis plan.
 - Analysis windows have been widened to capture as much information as possible. The Week 24 visit window will be further expanded to capture in-person visits for all participants.
 - Note: Per Protocol Version 3.0 this Cohort 5 will be closed (although it did not enroll 6 participants).

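### The Arm B Week 12 CD4+ change falls about 8 weeks after ART start and cannot be attributed to SAR441236; label it as post-ART and add a pre-ART summary

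*SAP*

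**What the plan says.** Secondary objective 4 (SAP 2.4.2) is "To evaluate the effects of single and multiple doses of SAR441236 on CD4+ T-cell counts". The matching outcome (SAP 3.2, item 4) is the change in CD4+ count "from baseline to week 12 following single dose of SAR441236 for all cohorts", with a per-infusion version for Cohort 4. SAP 4.2.2 analyses it with individual plots and numerical summaries by cohort. It does not mention ART start.

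Arm B is the viremic arm and has no placebo group (SAP 2.2). On ART timing, SAP 4.2.2 explains that the start "was changed from “by 28 days” (Version 3.0 or earlier) to “at 14 days” for Arm B participants". It then notes that "since no participants enrolled under Version 4.0, we consider maximum reduction occurring in up to 28 days of monotherapy for Arm B participants", so the 28-day rule is the one that applied. For Cohort 5 the COVID-19 Appendix (SAP 6.1) adds: "All participants had reached Day 28 and initiated ART by the end of February 2020".

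The HIV-1 RNA entries in SAP 4.2.2 do take ART into account. The Arm B plots stop at ART start, and maximum reduction is summarised "during monotherapy of SAR441236 (post-infusion and before ART initiation)".

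**The concern.** In Arms A and C, participants are already suppressed on ART at entry and have randomised placebo, so a Week 12 CD4+ change can be read against a stable background. In Arm B the same time point comes after two interventions: one antibody infusion, and then ART in a viremic person. Nothing in Arm B separates the two.

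SAP 1.1 says that secondary outcome results will be posted on ClinicalTrials.gov. Under the current wording, the Arm B figure would be posted as a change after a single dose of SAR441236, alongside cohorts on stable ART, with nothing to say that ART had started in between. The mixing could work in either direction: a rise could be misread as a benefit of the antibody, or a fall after the infusion could be hidden.

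**Working it through.** The SAP states no interval between ART start and Week 12, so there is no figure to reproduce. The check is a timeline.

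**Inputs**
- CD4+ time point: Week 12, Day 12 × 7 = 84 (SAP 3.2, item 4).
- Arm B Week 12 visit window: ±7 days, Days 77 to 91 (SAP 4.1.2).
- Latest ART start under the rule that applied to enrolled participants: Day 28 (SAP 4.2.2).
- Participants: Cohort 5 had four on study during the pause and one already off study, 4 + 1 = 5 (SAP 6.1). Cohort 8 had 2 (SAP 4.2.2). Total 5 + 2 = 7.

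**Formulas**
- Days on ART = visit day − ART start day.
- Share of the interval on ART = days on ART ÷ visit day.

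**Results for ART start on Day 28**

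| Week 12 visit | Days on ART | Weeks on ART | Share of interval |
|---|---|---|---|
| Early edge, Day 77 | 77 − 28 = 49 | 7.0 | 49/77 = 64% |
| Nominal, Day 84 | 84 − 28 = 56 | 8.0 | 56/84 = 67% |
| Late edge, Day 91 | 91 − 28 = 63 | 9.0 | 63/91 = 69% |

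Day 28 is the latest start that the rule allows, so an earlier start lengthens each of these intervals.

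**Analysis windows.** SAP 4.1.2 widens visit windows to the midpoints between successive expected evaluations. The documents supplied do not show the CD4+ schedule. If CD4+ is assumed at Weeks 8, 12 and 24, the Week 12 window runs from (8 + 12)/2 = Week 10 to (12 + 24)/2 = Week 18. That is 10 − 4 = 6 to 18 − 4 = 14 weeks after a Day 28 start, so every value in the window is still post-ART.

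**The Day 14 rule.** Under protocol Version 4.0, "participants in Arm B will initiate or re-initiate combination non-study-provided ART on Day 14". That would give 84 − 14 = 70 days, or 70/84 = 83%. Nobody enrolled in Arm B under that version, so this figure describes no participant.

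**Side by side.** For the same Arm B participants, SAP 4.2.2 limits the HIV-1 RNA plots and maximum reduction to before ART, but takes CD4+ to Week 12 without a limit, a label or a mark at ART start.

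**The case against.** The strongest reply is that no attribution is planned. CD4+ is described by cohort, with no test, no estimated drug effect and no contrast between Arm B and the other arms. The outcome's wording can be read as timing only. SAP 5.6 already reports when Arm B participants started ART, and the individual plots would show any CD4+ values taken before it. CD4+ enters none of the safety or de-escalation criteria in SAP 2.6, and the numbers are very small.

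Most of this stands, and it limits the weight of the point. It does not remove it: the figure serves an objective about the effects of SAR441236, and the ART start times in 5.6 are not linked to the CD4+ summary. A descriptive number still needs a label that fits what it measures.

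The reply also rightly blocks some stronger inferences. A reader might conclude that the Arm B change mainly reflects ART, or that a particular number of cells/mm³ would be wrongly credited to the antibody. The documents give no CD4+ response to ART, so neither follows. A reader might also conclude that objective 4 fails. It does not, because Arms A and C cover single and multiple doses with randomised placebo. Nor can every Arm B participant be counted as affected: SAP 6.1 says that some Cohort 5 Week 12 visits were virtual, with no labs.

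Finally, the outcome is taken from protocol section 10.2.2, and table and figure outlines sit in the Analysis Implementation Plan. Neither was available, so replacing the outcome would go further than the evidence allows.

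**Conclusion.** The point holds in a limited form. An on-schedule Arm B Week 12 CD4+ value follows at least about 8 weeks of ART (67% of the interval; 7 weeks at the early edge of the visit window). Without a control in Arm B, the change cannot be attributed to SAR441236. It concerns descriptive summaries in about seven participants, some of whom may have no Week 12 CD4+ value, and it leaves objective 4 answerable in Arms A and C.

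Two assumptions matter. The 8-week minimum assumes that the 28-day rule was kept. For Cohort 5 the SAP confirms that ART was started but gives a calendar limit, not individual study days; for Cohort 8 the supplied text gives the rule but no confirmation. The count of five in Cohort 5 is inferred from the COVID-19 Appendix. The timing of ART is a clinical matter and is not questioned here.

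**What to change.** Keep the protocol-specified Week 12 outcome, and make these changes in SAP 4.2.2 and in the posted results:

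1. Label the Arm B Week 12 CD4+ change as post-ART and not attributable to SAR441236.
2. Add a supplementary Arm B summary: change from baseline to the last post-infusion CD4+ value before ART initiation, up to Day 28.
3. Mark ART start on the Arm B CD4+ plots.
4. If no post-infusion, pre-ART CD4+ sample was collected, state that Arm B does not inform objective 4.

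Arms A and C are unchanged, and no visit or treatment rule is affected. The cost is some wording, one derived variable and a plot marker, using the ART start times already reported under SAP 5.6. The downside is shorter follow-up in the pre-ART summary: at most 28 of the 84 days, or one third.

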4.1 General Considerations

4.1.1 Analysis populations

In all cohorts, participants who do not receive study treatment or who receive less than 90% of their first or only intended infusion or SC injection dose will be replaced. Arm A or Arm C participants

who discontinue the study prior to Day 14 without having met the primary safety endpoint, will be replaced to ensure enough safety data are available for dose escalation evaluation. Arm B participants who discontinue the study prior to Day 14 without sufficient virology (as judged by the CST) **or have HIV-1 RNA < 5000 copies/mL at study entry** will be replaced to ensure enough efficacy data are available for dose de-escalation evaluation. The CST may decide on additional replacements if primary endpoints cannot be adequately assessed due to missing data or incorrect infusion procedure. Participants who initiate the infusion or SC injection but receive less than 90% of their first or only intended dose will be encouraged to remain on study and complete all study follow-up.

Safety population: All participants who have been exposed to SAR441236 or placebo.

Efficacy population: In by-cohort analyses, all participants who actually receive **≥0.9 mg/kg SAR441236 and have an entry plasma HIV-1 RNA ≥ 5000 copies/mL**. These participants should have efficacy measures that are sufficient and interpretable.

PK population: All participants who have been exposed to SAR441236 and have evaluable levels of SAR441236 such that PK parameters can be derived.

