For the primary efficacy analyses for Arm B cohorts, reduction in plasma HIV-1 RNA (\log_{10} copies/mL) from baseline to Day 7 will be summarized, both in a combined cohort and in each cohort separately. The comparison between pre- and post-treatment will be carried out using a paired t-test with 2-sided 95% confidence interval for the combined cohort, and a Wilcoxon signed rank test for each cohort separately. The analyses will use the Efficacy population defined in Section 4.1.1. **Sensitivity analysis will be carried out using a Wilcoxon signed rank test for the combined cohort.**

Sensitivity analysis including the Safety population as defined in Section 4.1.1 will be conducted.

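### The fixed 0.9 mg/kg floor for the by-cohort Efficacy population is 90% of the Cohort 5 dose but only 3% of the Cohort 8 dose

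*SAP*

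**What the plan says.** The definition in SAP 4.1.1 begins "Efficacy population: In by-cohort analyses, all participants who actually receive" and continues "≥0.9 mg/kg SAR441236 and have an entry plasma HIV-1 RNA ≥ 5000 copies/mL". The next sentence asks that these participants' efficacy measures be adequate and open to interpretation. It names no dose.

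The intended doses are in SAP 2.2: "Cohort 5: 1 mg/kg of SAR441236 administered as a single IV infusion" and "Cohort 8: 30 mg/kg of SAR441236 administered as a single IV infusion". Cohort 7 (10 mg/kg) never opened.

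SAP 4.1.1 also has a relative dose threshold, for a different purpose. In all cohorts, those "who receive less than 90% of their first or only intended infusion or SC injection dose will be replaced". Section 2.5 repeats this. People who start treatment but fall short of that threshold "will be encouraged to remain on study and complete all study follow-up".

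SAP 4.2.1 summarises the primary Day 7 change in HIV-1 RNA "both in a combined cohort and in each cohort separately", and adds: "The analyses will use the Efficacy population defined in Section 4.1.1". A sensitivity analysis uses the broader Safety population. SAP 4.2.2 carries similar analyses to Day 14 and gives the size of Cohort 8 as two.

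**The concern.** A dose criterion for a by-cohort analysis should mean roughly the same thing in each cohort. This one means nearly the full dose in Cohort 5 and at least 3% of the dose in Cohort 8. A Cohort 5 participant given 0.89 mg/kg (89% of intended) is left out, while a Cohort 8 participant given 0.9 mg/kg, less than the nominal Cohort 5 dose, meets the criterion.

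The case can arise under the plan, because under-dosed participants are asked to stay in follow-up and their HIV-1 RNA data would exist. What is at stake is the descriptive Cohort 8 estimate, in a study whose third hypothesis (SAP 2.3) is dose-dependent activity.

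There is a smaller gap in the wording. Section 4.1.1 frames the population for by-cohort analyses, but 4.2.1 uses it for the combined analysis as well. No dose criterion is stated specifically for the combined analysis.

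**Working it through.** **Inputs.** Floor: 0.9 mg/kg (SAP 4.1.1). Intended doses: 1, 10 and 30 mg/kg for Cohorts 5, 7 and 8 (SAP 2.2). Relative threshold used for replacement: 90% of the intended dose (SAP 2.5 and 4.1.1). Cohort 8 size: 2 (SAP 4.2.2).

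**Step 1: where the stated floor comes from numerically.** 0.90 × 1 mg/kg = 0.9 mg/kg, so the figure reproduces exactly from the Cohort 5 dose. It does not reproduce from the other Arm B doses: 0.90 × 10 = 9 mg/kg and 0.90 × 30 = 27 mg/kg.

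**Step 2: the floor as a share of each intended dose** (share = 0.9 / intended dose).

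| Cohort | Intended dose (mg/kg) | 0.9 mg/kg as share of dose | 90% of dose (mg/kg) | Gap (mg/kg) |
|---|---|---|---|---|
| 5 | 1 | 90% | 0.9 | 0 |
| 7 (never opened) | 10 | 9% | 9 | 8.1 |
| 8 | 30 | 3% | 27 | 26.1 |

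**Step 3: who is affected.** In Cohort 8, received doses from 0.9 to just under 27 mg/kg (3% to just under 90% of intended) satisfy the floor while falling below the 90% mark. That span is 27 − 0.9 = 26.1 mg/kg, or 26.1/30 = 87% of the intended dose. Such a participant would be replaced under the enrolment rule and, with entry HIV-1 RNA of at least 5000 copies/mL, would still meet the stated Efficacy population criteria on dose and viral load. In Cohort 5 the two thresholds coincide.

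**Step 4: can a test result change?** The by-cohort test is the Wilcoxon signed rank test. Its smallest exact two-sided p is 2/2^n:

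- n = 2: 2/4 = 0.50
- n = 1: 2/2 = 1.00

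Whether Cohort 8 is analysed with two participants or one, the test cannot approach significance. Only the descriptive summary can move, and the documents give no figures from which to say by how much.

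**The case against.** The strongest reply is that no stated rule is broken. The 90% threshold decides who is replaced, not whose data are analysed, and the SAP never says the two must agree. That stands. A reader might infer that section 4.1.1 contradicts itself; it does not. A reader might also infer that an under-dosed Cohort 8 participant would enter the summary outside any rule. In fact the floor is a rule, and it still removes anyone below 0.9 mg/kg. The fair complaint is that it is far more lenient in Cohort 8 than in Cohort 5.

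Second, the sentence on adequate and interpretable efficacy measures could be used to exclude a grossly under-dosed participant. It might support that, but it concerns the measurements and sets no dose level, so it leaves the decision to judgement.

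Third, the SAP does not say how a partially dosed participant is labelled in by-cohort summaries. Grouping by enrolled cohort is the likely reading. Coding details belong to the Analysis Implementation Plan (SAP 1.1), which was not available, so this point concerns the SAP wording only.

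Fourth, disclosure is already planned. Section 5.5 requires the actual dose for any partial infusion, and section 4.2.2 requires individual HIV-1 RNA and concentration plots. With two participants, these would largely reveal the problem. That stands and limits the severity, although disclosure does not settle who belongs in the summary.

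Finally, redefining a population after enrolment has closed, in an open-label arm, is itself a late change. That is fair, and the fix should say so openly.

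**Conclusion.** The point holds as a minor defect of definition. A single floor of 0.9 mg/kg, tied to by-cohort analyses, works as a 90% criterion in Cohort 5 and a 3% criterion in Cohort 8, and the SAP gives no reason for using it in Cohort 8. Confidence in this mismatch is high, because it rests on exact arithmetic from the SAP's own figures.

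Any effect on results is conditional. It needs at least one of the two Cohort 8 participants to have received less than 27 mg/kg, and to have met the viral load criterion. A reader might infer that the 30 mg/kg summary is diluted by partial doses, but no document shows that either participant was under-dosed. If both received at least 27 mg/kg, the fixed and relative criteria select the same people and nothing changes.

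No claim is made about the combined Arm B estimate. The protocol text supplied contains no analysis-population section against which to check the SAP definition.

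**What to change.** In SAP 4.1.1, for by-cohort efficacy analyses, replace the 0.9 mg/kg floor with receipt of at least 90% of the cohort's intended dose, and keep the entry HIV-1 RNA criterion of at least 5000 copies/mL. State separately which dose criterion the combined Arm B analysis in 4.2.1 uses. A common 0.9 mg/kg exposure floor is acceptable there, because that analysis already mixes 1 and 30 mg/kg.

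Label the edit as a change made after enrolment closed. Whatever is decided about the wording, state in the report whether either Cohort 8 participant received less than 90% of the intended dose.

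The cost is one or two sentences, using dose data that section 5.5 already calls for. The dose criterion for Cohort 5 is unchanged. The downside is that the Cohort 8 by-cohort summary could fall from two participants to one; that person would remain in the Safety-population sensitivity analysis and in the individual plots. The change concerns who is analysed and has no bearing on dosing.
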